6.1 Gender

Table 1: Subject Gender by Febrile Status

Gender	Febrile (n=33)	Afebrile (n=75)	Total (n=108)
Male	10 (30%)	25 (33%)	35 (32%)
Female	23 (70%)	50 (67%)	73 (68%)

Subject gender distribution is comparable between febrile and afebrile subject groups.

6.2 Age

Table 2: Subject Age by Febrile Status

Age (years)	Febrile (n=33)	Afebrile (n=77)	Total (n=110)
Mean	44.91	44.73	44.78
Standard deviation	16.92	15.96	16.14

A **t-test for independent samples** revealed no statistically significant difference in mean age between febrile and afebrile subjects: $\mu_a - \mu_b = 0.18$; $t = +0.05$; $df = 108$; $p(\text{two-tailed}) = 0.96$ ($p > 0.05$).

Figure 1 below shows the age distribution of study subjects across the entire range.

[figure not shown]

Figure 1. Age distribution of study subjects.

6.3 Ethnicity

Table 3: Subject Ethnicity by Febrile Status

Ethnicity	Febrile (n=33)	Afebrile (n=77)	Total (n=110)
White – Non-Hispanic	7	9	16
White - Hispanic	6	22	28
Hispanic - Unspecified	6	20	26
African American	14	23	37
American Indian	-	2	2
Asian	-	1	1

The various population ethnicities were well represented across the subject sample.

7. Clinical Accuracy

Clinical Accuracy of the welloStationX thermometer was evaluated by comparing the first recorded measurement of the WelloStationX (DUT) with the single measurement recorded by the Welch Allyn SureTemp oral thermometer (reference thermometer).

7.1 Means and Standard Deviations

Table 4 below shows the mean and standard deviation of temperature readings in °F with the welloStationX (DUT) and the Welch Allyn SureTemp (reference thermometer) by febrile versus afebrile subject groups.

Table 4: Means and Standard Deviations by Febrile Status

Temperature Reading (°F)	welloStationX Febrile (n=33)	Welch Allyn Febrile (n=33)	welloStationX Afebrile (n=77)	Welch Allyn Afebrile (n=77)
Mean	99.83	99.58	98.15	98.22
Standard deviation	0.60	0.71	0.47	0.29

7.2 Clinical Bias

Agreement through clinical bias evaluation was calculated as the Mean Bias \pm SD by subtracting the first output measurement recorded with the welloStationX thermometer (DUT) from the corresponding output measurement recorded with the Welch Allyn SureTemp oral thermometer for each subject, and then calculating the Mean Bias \pm SD of the biases.

Table 5 below shows clinical bias by febrile status.

Table 5: Clinical bias by febrile status.

Mean bias \pm SD Febrile (n=33)	Mean bias \pm SD Afebrile (n=77)	Mean bias \pm SD All (n=110)
0.25 °F \pm 0.33	-0.06 °F \pm 0.42	0.03 °F \pm 0.42

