2.0 Device Description

The welloStationX is an automated No-Touch Self-Service Electronic Thermometer designed to provide an accurate temperature reading without the time and exposure of a skilled attendant to the possibility of infection.

The welloStationX is an electronic thermometer using an infrared sensor of the surface of the forehead adjusting human body skin temperature to oral thermometer without contact.

The welloStationX is being evaluated for use for the screening of individuals for fever.

Deatiled information on the configuration and operation of the welloStationX can be found in the accompanying welloStationX Use and Care Manual.

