The study was a non-randomized, non-blinded single arm design with the subject as his or her own control to evaluate the clinical accuracy of the welloStationX thermometer with respect to that of the standardized Welch Allyn SureTemp oral thermometer in the screening of individuals with fever.

4. Subject Sample

Subjects were 110 males and females aged 5 years of age and older: 33 subjects (30%) were febrile, with fever defined as a core temperature of 99.5°F (37.5°C) or higher; and 77 subjects were afebrile.

Subjects were recruited from amongst non-profit clinical sites and through social media posts for subjects to come to a test site or to be evaluated in his or her own home in the widespread Dallas/Fort Worth area.

Afebrile subjects were compensated with a \$10 gift card and febrile subjects were compensated \$25, the additional amount intended to assist the febrile subject to recovery.

5. Study Procedures

Each subject's temperature was measured three separate times sequentially using the study device, the WelloStationX® (*DUT*) and one time using a new off-the-shelf calibrated Welch Allyn SureTemp oral thermometer with disposable probe covers (the reference thermometer). Each measurement was recorded by a trained technician by following the instructions for use contained in the respective device labeling.

Subject age, gender and race were recorded for each subject, and potential adverse event observation was conducted.

A subject or the subject's guardian was immediately informed if a febrile temperature measurement (99.5°F (37.5°C) or higher) was recorded using the Welch Allyn SureTemp oral thermometer. The subject or guardian will be advised to consider seeking medical attention.

RESULTS

6. Sample Demographics

The sample demographics of gender, age and race are shown below in Tables 1 through 3, respectively, for febrile and afebrile subjects and for subjects overall.

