7.3 Limits of Agreement and Bland Altman Plots

The limits of agreement ($1.96 \times 1\text{SD}$) were calculated (+0.86, -0.80). From this and the mean bias and standard deviation values, a Bland Altman plot of agreement between the test thermometer (welloStationX) and the reference thermometer (SureTemp) in febrile and afebrile subjects was constructed and is shown in Figure 2 below.

Band Altman Plot for Febrile and Afebrile Subjects (n=110)

[figure not shown]

Figure 2: Bland Altman Plot of Agreement Between Study Thermometer (welloStationX) and Reference thermometer (SureTemp) in Febrile and Afebrile Subjects

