7.4 XY Plot and Correlation Coefficient

To further demonstrate the closeness of the relationship between the welloStationX (DUT) and the SureTemp (reference) readings, an XY plot of the two sets of readings was created and is shown in Figure 3 below.

[figure not shown]

Figure 3: XY Plot of welloStationX versus SureTemp for all subjects

$R^2 = 0.80$, indicating a strong linear relationship

8. Clinical Repeatability

Clinical Repeatability was calculated using the pooled standard deviations of the triplicate measurements recorded by the welloStationX.

Table 5 below shows clinical repeatability by febrile status.

Table 5: Clinical repeatability of the welloStationX by febrile status.

Febrile (n=33)	Afebrile (n=77)	All (n=110)
0.13	0.09	0.06

9. Safety Evaluation

There were no observed or reported adverse events for any subject in the study.

DISCUSSION

The results of this clinical study are interpreted both with respect to the study dataset alone and compared to the research data published in the following whitepaper:

Clinical validation of the CAREGIVER® non-contact thermometer model PRO-TF200/PRO-TF300 in febrile and afebrile patients of all ages

Naja E. [name], Alice Huang & Gary O'Hara MSE

November 2013 Copyright ©2013 Thermomedics®, Inc.

This comparison was selected for the following reasons:

1. The reported study clinical data was that which was submitted to the FDA in support of market clearance for the Caregiver Professional Clinical Thermometer (K131771) which is the predicate device in the current submission for K180298.
2. In the reported study, the reference thermometer used was the Welch Allyn SureTemp oral thermometer, the same reference thermometer used in the welloStationX clinical precision study.

There were no notable differences in gender, age or ethnicity by febrile status and age distributions across the spectrum was well represented. Therefore, the subject population was across febrile status was homogenous and the sample overall representative of the intended patient population.

The limits of agreement for the welloStationX are (+0.86, -0.80) which is better than that for the Caregiver study whose limits of agreement was (+0.82, -1.21).

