From the Bland Altman Plot, it is found that only four data points lie just outside the limits of agreement (such that 96.4% of all data points lie within the limits of agreement) which indicates there is a strong agreement between the performance of the welloStationX and the SureTemp and is fewer than the six outliers found in the Caregiver study, most of which also lay further away from the limits of agreement than the four outliers in the welloStationX study.

The limits of agreement did not exceed 0.86 (absolute value) and clinical bias did not exceed 0.03°F for the study population overall. These strong indicators of the close agreement between the performance of the welloStationX and the SureTemp are also superior to those attained in the Caregiver study, where the limits of agreement did not exceed 1.21 (absolute value) and clinical bias did not exceed 0.20 °F for subjects overall.

The highest bias attained was 0.25°F for subjects in the welloStationX febrile subject group, which is still notably lower than the greatest bias attained in the Caregiver study of 0.32°F for subjects in the afebrile group.

The XY Chart further demonstrates the close agreement between the performance of the welloStationX and the SureTemp. The correlation coefficient of 0.80 supports this strong linear relationship.

The notably low clinical repeatability of 0.062 for subjects overall indicates that the absolute difference in repeat measurements taken with the welloStationX is very low and therefore precision across repeated temperature readings is very strong and highly repeatable. Clinical repeatability was comparably high for both the febrile and afebrile subject groups in the welloStationX study, at 0.13 and 0.09, respectively. Each of these clinical repeatability values for the welloStationX thermometer is notably lower than those attained for the Caregiver (0.17 for subjects overall; 0.21 for the febrile subject group and 0.15 for the afebrile subject group).

CONCLUSION

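### Report Section 7.2 defines clinical bias as reference minus device, but the printed biases and limits of agreement carry the sign of device minus reference

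*SAP*

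**What the plan says.** The SAP document is a completed results report. Its Section 7.2 describes clinical bias as the mean and SD of differences formed by "subtracting the first output measurement recorded with the welloStationX thermometer (DUT) from the corresponding output measurement recorded with the Welch Allyn SureTemp oral thermometer". The clinical bias table that follows (Table 5 in 7.2; a second Table 5, on repeatability, appears in Section 8) prints +0.25 ± 0.33°F for febrile subjects, -0.06 ± 0.42°F for afebrile subjects and +0.03 ± 0.42°F for all.

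Section 7.1 says that "Table 4 below shows the mean and standard deviation of temperature readings in °F" for each device. The febrile means are 99.83 (welloStationX) and 99.58 (Welch Allyn); the afebrile means are 98.15 and 98.22.

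Section 7.3 says that the limits of agreement "were calculated (+0.86, -0.80").

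Protocol Section 4.2 asks for mean bias and limits of agreement and fixes no direction for the difference.

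On grouping, report Section 4 says that "33 subjects (30%) were febrile, with fever defined as a core temperature of 99.5°F (37.5°C) or higher". It does not name the device that assigned subjects to the groups, and neither does Protocol Section 3.2.

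**The concern.** To subtract the device from the reference is to compute reference minus device. Under that rule a positive febrile bias means that the device reads low. Table 4 shows the device mean above the reference mean in febrile subjects. Both cannot be right.

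Protocol Section 2.0 states: "The welloStationX is being evaluated for use for the screening of individuals for fever". For that use the sign carries the practical meaning. At a fixed threshold, a device that under-reads febrile people tends to miss fevers, and one that over-reads them does not miss fevers for that reason. No sentence in the report states the direction. The Discussion gives only the size: "The highest bias attained was 0.25°F for subjects in the welloStationX febrile subject group". A reader who works from 7.2 and a reader who works from 7.1 reach opposite conclusions about the febrile group.

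The Discussion also sets the signed limits beside those of the comparator device, "which is better than that for the Caregiver study whose limits of agreement was (+0.82, -1.21"). The upper limit is +0.86 or +0.80 depending on the convention, so it lies outside or inside +0.82. The comparator's own sign convention is not given.

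**Working it through.** **Inputs.** Table 4: febrile (n=33) device 99.83, reference 99.58, reference SD 0.71; afebrile (n=77) device 98.15, reference 98.22. Table 5 in 7.2: +0.25 (SD 0.33), -0.06 (SD 0.42), +0.03 (SD 0.42). Section 7.3: limits +0.86 and -0.80, multiplier 1.96.

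**Step 1: reproduce the printed figures.** In the same subjects, the mean paired difference equals the difference of the two means. The overall value is (33 × febrile + 77 × afebrile)/110.

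| | Device - reference | Reference - device (rule in 7.2) | Printed |
|---|---|---|---|
| Febrile | 99.83 - 99.58 = +0.25 | -0.25 | +0.25 |
| Afebrile | 98.15 - 98.22 = -0.07 | +0.07 | -0.06 |
| All | (33 × 0.25 - 77 × 0.07)/110 = +0.026 | -0.026 | +0.03 |

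All three printed signs follow device minus reference. The printed group values also agree with the printed overall value: (33 × 0.25 - 77 × 0.06)/110 = +0.033.

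**Step 2: limits of agreement.** Midpoint (0.86 - 0.80)/2 = +0.03; half-width (0.86 + 0.80)/2 = 0.83; 0.83/1.96 = 0.423, which agrees with the printed SD of 0.42. The limits therefore follow the table and not the rule in the text. Under the rule as written they would be +0.80 and -0.86.

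**Step 3: rounding.** Each mean is given to 0.01, so a difference can be off by at most 0.01. Under the rule in 7.2 the febrile value lies between -0.26 and -0.24 and the afebrile value between +0.06 and +0.08. Neither range includes the printed value. Under device minus reference the afebrile range is -0.08 to -0.06, so the gap between -0.07 and the printed -0.06 is rounding and not a separate error.

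**Step 4: which element is wrong?** Reversing the phrase in 7.2 reconciles everything. The alternative is that the rule is right and Table 4 is mislabelled. Reference minus device after swapping labels gives:

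| Labels swapped | Febrile | Afebrile | All |
|---|---|---|---|
| Febrile pair only | +0.25 | +0.07 | (8.25 + 5.39)/110 = +0.124 |
| Afebrile pair only | -0.25 | -0.07 | -0.124 |
| Both pairs | +0.25 | -0.07 | (8.25 - 5.39)/110 = +0.026 |

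Only the double swap matches the printed table.

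**Step 5: a conditional check on the labels.** Suppose that every febrile subject had a reference reading of at least 99.5°F. For n values with that floor, the largest possible sample SD is (mean - 99.5) × √n. With mean 99.58 and n=33 this is 0.08 × 5.745 = 0.46, or 0.085 × 5.745 = 0.49 allowing for rounding of the mean. Table 4 prints 0.71. With a mean of 99.83 the bound is 0.33 × 5.745 = 1.90, so either printed febrile SD would be possible. The documents do not state the supposition, and a misprinted SD is another possibility.

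**Step 6: size.** Febrile standard error 0.33/√33 = 0.057; with t on 32 df the half-width is 0.117, so the 95% CI for the absolute bias is 0.13 to 0.37°F and excludes zero. Febrile limits, as device minus reference, are 0.25 ± 1.96 × 0.33 = -0.40 to +0.90°F if the wording is at fault, or -0.90 to +0.40°F if the labels are.

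**The case against.** The strongest reply is that no calculation has been shown to be wrong. Read as device minus reference, both tables and the limits agree, and one subtract-this-from-that phrase is out of line. Table 4 stands just above it with labelled means, so an attentive reader sees the direction first. The success statement in Protocol Section 4.3 has no signed margin, and the Discussion argues largely from absolute values. Figures 2 and 3 are missing from the text available here, and their axes may show the direction.

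Much of this stands. The bias size, SD, limits' width (1.66), R-squared and absolute-value comparisons with the comparator are unaffected. The inside-or-outside point about +0.82 cannot be settled without the comparator's sign convention. The febrile limits and confidence interval in this note are derived here and are not reported values.

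The SD bound is also open to challenge. Protocol Section 3.3.5 and report Section 5 apply 99.5°F to SureTemp readings, but as a rule for notifying subjects, not as a stated grouping rule. The bound is a reason to check the labels and does not show that they are wrong.

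The contradiction remains. It concerns the stated rule for a primary outcome, the febrile sign is not attached to noise, and figures that show a direction would not reconcile the text with the tables.

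**Conclusion.** The concern holds. The rule in 7.2 reverses the sign of all three printed biases and of the centre of the limits, and rounding cannot account for it. In device-minus-reference terms the febrile bias is +0.25°F or -0.25°F, depending on which element is in error.

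That the passages conflict is certain from the printed numbers. The cause is not. A reversed phrase is the simplest explanation, because one wording change reconciles every figure and leaves the device reading 0.25°F high in febrile subjects. A swap of labels in both Table 4 pairs is not excluded and would leave it reading 0.25°F low. The argument that lends the swap some weight assumes that febrile status was assigned from recorded reference readings of at least 99.5°F.

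This should be fixed. It does not change the size of any agreement statistic, but the report currently supports two opposite statements about febrile subjects.

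**What to change.** 1. Check the Table 4 device labels and the febrile reference SD of 0.71 against subject-level data, and establish which device's reading classified fever.
2. Correct whichever element is wrong: the sentence in 7.2 or the Table 4 labels. The sentence should not be edited without the check, because that could fix the wrong direction in place.
3. Use device minus reference for the bias table, the limits and the Bland-Altman plot, and state that convention once.
4. Add a sentence saying whether the device reads high or low in febrile subjects.

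The cost is a source-data check and one corrected sentence or one relabelled table, plus the added statement. The bias table, limits and plot need reissue only if the labels were wrong and their signs change. No new data are needed.

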7.3 Limits of Agreement and Bland Altman Plots

The limits of agreement ($1.96 \times 1\text{SD}$) were calculated (+0.86, -0.80). From this and the mean bias and standard deviation values, a Bland Altman plot of agreement between the test thermometer (welloStationX) and the reference thermometer (SureTemp) in febrile and afebrile subjects was constructed and is shown in Figure 2 below.

Band Altman Plot for Febrile and Afebrile Subjects (n=110)

[figure not shown]

Figure 2: Bland Altman Plot of Agreement Between Study Thermometer (welloStationX) and Reference thermometer (SureTemp) in Febrile and Afebrile Subjects

7.4 XY Plot and Correlation Coefficient

To further demonstrate the closeness of the relationship between the welloStationX (DUT) and the SureTemp (reference) readings, an XY plot of the two sets of readings was created and is shown in Figure 3 below.

[figure not shown]

Figure 3: XY Plot of welloStationX versus SureTemp for all subjects

$R^2 = 0.80$, indicating a strong linear relationship

8. Clinical Repeatability

Clinical Repeatability was calculated using the pooled standard deviations of the triplicate measurements recorded by the welloStationX.

Table 5 below shows clinical repeatability by febrile status.

Table 5: Clinical repeatability of the welloStationX by febrile status.

Febrile (n=33)	Afebrile (n=77)	All (n=110)
0.13	0.09	0.06

9. Safety Evaluation

There were no observed or reported adverse events for any subject in the study.

DISCUSSION

The results of this clinical study are interpreted both with respect to the study dataset alone and compared to the research data published in the following whitepaper:

Clinical validation of the CAREGIVER® non-contact thermometer model PRO-TF200/PRO-TF300 in febrile and afebrile patients of all ages

Naja E. [name], Alice Huang & Gary O'Hara MSE

November 2013 Copyright ©2013 Thermomedics®, Inc.

This comparison was selected for the following reasons:

1. The reported study clinical data was that which was submitted to the FDA in support of market clearance for the Caregiver Professional Clinical Thermometer (K131771) which is the predicate device in the current submission for K180298.
2. In the reported study, the reference thermometer used was the Welch Allyn SureTemp oral thermometer, the same reference thermometer used in the welloStationX clinical precision study.

There were no notable differences in gender, age or ethnicity by febrile status and age distributions across the spectrum was well represented. Therefore, the subject population was across febrile status was homogenous and the sample overall representative of the intended patient population.

The limits of agreement for the welloStationX are (+0.86, -0.80) which is better than that for the Caregiver study whose limits of agreement was (+0.82, -1.21).

From the Bland Altman Plot, it is found that only four data points lie just outside the limits of agreement (such that 96.4% of all data points lie within the limits of agreement) which indicates there is a strong agreement between the performance of the welloStationX and the SureTemp and is fewer than the six outliers found in the Caregiver study, most of which also lay further away from the limits of agreement than the four outliers in the welloStationX study.

The limits of agreement did not exceed 0.86 (absolute value) and clinical bias did not exceed 0.03°F for the study population overall. These strong indicators of the close agreement between the performance of the welloStationX and the SureTemp are also superior to those attained in the Caregiver study, where the limits of agreement did not exceed 1.21 (absolute value) and clinical bias did not exceed 0.20 °F for subjects overall.

The highest bias attained was 0.25°F for subjects in the welloStationX febrile subject group, which is still notably lower than the greatest bias attained in the Caregiver study of 0.32°F for subjects in the afebrile group.

The XY Chart further demonstrates the close agreement between the performance of the welloStationX and the SureTemp. The correlation coefficient of 0.80 supports this strong linear relationship.

The notably low clinical repeatability of 0.062 for subjects overall indicates that the absolute difference in repeat measurements taken with the welloStationX is very low and therefore precision across repeated temperature readings is very strong and highly repeatable. Clinical repeatability was comparably high for both the febrile and afebrile subject groups in the welloStationX study, at 0.13 and 0.09, respectively. Each of these clinical repeatability values for the welloStationX thermometer is notably lower than those attained for the Caregiver (0.17 for subjects overall; 0.21 for the febrile subject group and 0.15 for the afebrile subject group).

CONCLUSION

The intent of this study was to clinically validate application of the welloStationX automated no-contact thermometer to the reference device, the Welch Allyn SureTemp oral thermometer. The validation results indicate a high level of agreement between the welloStationX and the SureTemp. Repeatability across three sequential measurements with the welloStationX indicated high precision. It can be concluded that the welloStationX automated non-contact thermometer is an accurate and reliable tool to measure body temperature of individuals five years of age and older.

END OF DOCUMENT

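### Coverage of the study's own 1.96-SD limits, and four outliers against six, do not show strong agreement; limits by febrile status are missing, and Table 4 must first be reconciled with the text

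*SAP*

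**What the plan says.** Protocol 4.3 makes close agreement with the SureTemp the test of success, with agreement values at least comparable to those published for the Caregiver. It sets no numeric limit. Protocol 4.2 lists mean bias with SD, limits of agreement and a Bland-Altman plot, and asks for all analyses by febrile status, as applicable.

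Report section 7.3 states that the limits, at 1.96 SD, "were calculated (+0.86, -0.80"; this is one pair for all 110 subjects. The Discussion then argues in four ways:

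- coverage: "96.4% of all data points lie within the limits of agreement) which indicates there is a strong agreement";
- outlier count: the welloStationX's four "is fewer than the six outliers found in the Caregiver study". The same sentence adds a remark on how far Caregiver's outliers fell beyond its limits: "most of which also lay further away from the limits of agreement than the four outliers in the welloStationX study";
- limits: the pooled pair, "which is better than that for the Caregiver study whose limits of agreement was (+0.82, -1.21";
- largest subgroup bias: 0.25°F (febrile), "which is still notably lower than the greatest bias attained in the Caregiver study of 0.32°F for subjects in the afebrile group".

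Report section 7.2 defines the bias as "subtracting the first output measurement recorded with the welloStationX thermometer (DUT) from the corresponding output measurement" on the SureTemp, that is, reference minus device. Its Table 5 prints 0.25 ± 0.33 (febrile, n=33), -0.06 ± 0.42 (afebrile, n=77) and 0.03 ± 0.42 (all). Table 4 in section 7.1 gives the "mean and standard deviation of temperature readings in °F with the welloStationX (DUT) and the Welch Allyn SureTemp (reference thermometer" by group.

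Protocol 3.2 and report section 4 define fever as a core temperature of at least 99.5°F. Protocol 3.3.5 applies the same cut-off to the SureTemp reading, as a rule for informing the subject.

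**The concern.** Limits of agreement estimated from a sample are built to contain about 95% of that sample. Finding 96.4% inside them describes the shape of the differences and not their size; a much less precise device would score the same. The outlier count has the same flaw. Since Protocol 4.3 gives no numeric criterion, the conclusion depends on the quality of the supporting argument, and one stated support carries no information. The figures that do carry information, the size of the bias and limits, have no confidence intervals.

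The device is evaluated for fever screening, and the pooled bias of 0.03°F averages a febrile 0.25 with an afebrile -0.06. Limits by group would show this, but the text omits them.

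Those limits cannot yet be read as performance in fever. As Table 4 is labelled, the device reads 0.25°F above the reference in febrile subjects. By the definition in section 7.2, the printed +0.25 means that it reads 0.25°F below.

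**Working it through.** **1. The report's own figures.** Share inside: (110 - 4)/110 = 96.4%, as printed. Limits: 0.03 ± 1.96 × 0.42 = -0.79 to +0.85. The printed -0.80 and +0.86 imply SD = 1.66/3.92 = 0.4235, so they agree within rounding. The groups combine to (33 × 0.25 - 77 × 0.06)/110 = 0.033 with SD 0.419, matching 0.03 ± 0.42.

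**2. Coverage.** In 100,000 normal samples of 110 at each SD, with the limits re-estimated in every sample:

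| True SD (°F) | Mean share inside | Mean number outside | P(4 or fewer outside) |
|---|---|---|---|
| 0.2 | 95.2% | 5.3 | 0.29 |
| 0.42 | 95.2% | 5.3 | 0.29 |
| 1.0 | 95.2% | 5.3 | 0.29 |

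The central 95% range is 2 to 8 points outside. Heavy-tailed or skewed differences give about 94.6 to 94.8%, and uniform differences about 99.9%. Coverage changes with shape and not with SD.

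**3. Outlier count.** 4/110 = 3.6%. Caregiver's N is not given. Under assumed values, six outliers are 5.7% of 105, 3.6% of 165 and 3.0% of 200. The remark on how far outliers lay beyond the limits does concern size, but no distance in °F is given for either study.

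**4. Figures that bear on agreement, with 95% intervals.** Bias: mean ± t × SD/√n. Each limit: SE = SD × √(1/n + 1.96²/(2(n - 1))), multiplied by t on n - 1 degrees of freedom. Pooled SE of a limit: 0.42 × √(1/110 + 3.8416/218) = 0.0686.

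| | Bias | Lower limit | Upper limit |
|---|---|---|---|
| All | 0.03 (-0.05 to 0.11) | -0.80 (-0.94 to -0.66) | 0.86 (0.72 to 1.00) |
| Febrile, provisional | 0.25 (0.13 to 0.37) | -0.40 (-0.60 to -0.19) | 0.90 (0.69 to 1.10) |
| Afebrile, provisional | -0.06 | -0.88 (-1.05 to -0.72) | 0.76 (0.60 to 0.93) |

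The group limits come from Table 5 in section 7.2: 0.25 ± 1.96 × 0.33 and -0.06 ± 1.96 × 0.42. Each pair has one end beyond the pooled maximum of 0.86.

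**5. Table 4 against the text.** Its printed means and SDs are: welloStationX febrile 99.83 (0.60), SureTemp febrile 99.58 (0.71), welloStationX afebrile 98.15 (0.47), SureTemp afebrile 98.22 (0.29).

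- Direction: reference minus device is 99.58 - 99.83 = -0.25, but Table 5 prints +0.25.
- Spread: if all n readings are at or above a floor T with mean m, the SD is at most (m - T)√n, reached with n - 1 readings on the floor and one high. Here 0.08 × √33 = 0.46, or 0.085 × √33 = 0.49 with the mean at its rounding limit. The table prints 0.71.
- Working back from SD ≥ 0.705 and mean ≤ 99.585, the lowest reading is at most 99.585 - 0.705/√33 = 99.46°F.
- Exchanged column labels: reference minus device becomes 99.83 - 99.58 = +0.25 and 98.15 - 98.22 = -0.07 (printed -0.06, within rounding). The maximum SD becomes 0.33 × √33 = 1.90, against 0.60. Both conflicts vanish.

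**6. Caregiver comparison.** Width: 0.86 + 0.80 = 1.66 against 0.82 + 1.21 = 2.03°F. Largest limit: 0.86 against 1.21. Overall bias: 0.03 against 0.20. None of these depends on sign. Limit by limit, sign matters: as printed, 0.86 is slightly further out than 0.82 while 0.80 is closer than 1.21; with Caregiver's signs reversed, both welloStationX limits are closer (0.86 against 1.21, 0.80 against 0.82). Caregiver's direction of subtraction is not stated.

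**The case against.** The strongest reply is that the headline concerns one argument in the Discussion. Protocol 4.3 does not use coverage or outlier counts, and the Discussion separately compares the size of bias and limits, which favours the welloStationX. That stands. A reader might infer that close agreement has not been shown or that the comparison fails; the documents do not support this.

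A reader might also infer from Table 4 that section 7.2 misdescribes the bias, that febrile subjects were misclassified, or that close to half of them (about 46%, if SureTemp readings were roughly normal) were below 99.5°F. None of this is established. Exchanged labels in Table 4 would remove both conflicts and leave section 7.2 correct. Fever is defined by core temperature, Protocol 3.3.5 is only a notification rule, and how subjects were classed is not stated. What stands is that the labels, the definition and a SureTemp cut-off of 99.5°F cannot all hold together.

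On group limits, Protocol 4.2 says as applicable, bias and SD are printed by group, and Figure 2 is not available, although its caption describes one combined plot. The omission is therefore modest and easily repaired. The protocol names no confidence intervals for limits; asking for them is good practice and does not show a departure from plan.

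The 0.25 against 0.32°F sentence openly compares maxima in different groups and is true of the point estimates. Only 'notably' lacks support: the febrile interval is 0.13 to 0.37, and Caregiver's uncertainty is not given.

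**Conclusion.** The point holds and should be fixed. Neither 96.4% coverage nor four outliers against six is evidence of close agreement. The coverage result assumes roughly normal differences and does not depend on the SD; the outlier percentages for Caregiver rest on assumed sample sizes.

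Limits by febrile status are absent from the text. Those derived here are provisional. Either the Table 4 labels are exchanged, or the direction of the bias is misdescribed and at least one subject grouped as febrile read 99.46°F or lower on the SureTemp. The documents do not settle which.

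The pooled bias, width and largest limit do not depend on the grouping or on sign, so the overall conclusion is narrowed and not reversed.

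**What to change.** Leave Protocol 4.3 as written and correct the report.

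1. Withdraw the coverage and outlier-count inferences. Rest the agreement statement on the size of the bias and limits, with 95% intervals. Keep the remark on outlier distance only if distances in °F are given for both studies.
2. Check Table 4's labels, the direction of subtraction and the febrile classification against source data. Reconcile Protocol 3.2 and 3.3.5 with report sections 4, 7.1 and 7.2, without presuming which is wrong, and state how subjects were classed.
3. Then report limits of agreement by febrile status with intervals.
4. Present the Caregiver comparisons as descriptive comparisons of point estimates, drop 'notably', compare like groups where Caregiver's values are available, and confirm its sign convention before comparing limit by limit.

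The cost is some rewording, a check of source data and a small re-analysis of data already held. The comparative claim becomes weaker, and group results may change if labels or classifications are corrected.
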